1. INTERVENTION GROUP

A CT-scan may be acquired for patients in the intervention group as part of the pre-operative planning. Patients will undergo surgical open reduction and internal fixation (ORIF) with a volar locking plate and/or dorsal plate. An additional cast may be applied for a maximum of 2 weeks post-surgery for wound protection. Patients are instructed to use their wrist as pain allows for. Patients are referred for physical therapy at the discretion of their treating physician or according to local protocol.

2. CONTROL GROUP

[figure not shown]
The conservatively treated patient group receives a permanent circular cast between 1 and 2 weeks after trauma. The total duration of cast treatment may vary between 4-6 weeks according to local protocol. Vitamin C 500mg may be prescribed to prevent complex regional pain syndrome (CRPS) according to local protocols. Patients are referred for physical therapy according to local protocol or at the discretion of their treating physician. Unless there is a strong clinical indication, it is not possible for patients in the conservative arm to crossover to the operative group during the period of cast treatment (worsening of radiographic fracture characteristics or pain complaints during cast treatment are not criteria for crossover).

Use of co-intervention (if applicable)

Not applicable

Escape medication (if applicable)

Not applicable

6. METHODS

6.1 Study parameters/endpoints

6.1.1 Primary study outcome

Response variable:

- Wrist function as reported by the patient (Patient-Rated Wrist Evaluation score (PRWE)) 1 year after trauma

6.1.2 Secondary study outcomes

Response variable:

1) Change in:

- Wrist function as reported by the patient (Disabilities of the Arm, Shoulder and Hand (DASH))
- Quality of life as reported by the patient (EQ-5D)
- Costs evaluation questionnaire
- ROM (range of motion)
- Complications
- Grip strength

Explanatory variable:

- Radiographic parameters (dorsal tilt, radial inclination, radial shortening, fracture union, and posttraumatic arthritis.)
- Frailty score
- Patient reported pain catastrophizing (Pain Catastrophizing Scale (PCS))

6.2 Randomization, blinding and treatment allocation

Upon obtaining informed consent, patients will be randomized into either the intervention group (open reduction and internal fixation) or the control group (closed reduction and plaster immobilization). In order to avoid any imbalance between treatment groups, patients will be randomized in 2 strata using a block randomization. Two strata according to age: 65-75 and over 75 years of age. Randomization will be performed by means of a computerized randomization.

6.3 Study procedures

For a detailed description of the treatment in both groups see above. For a schedule of follow-up visits see table 1. Study procedures additional to standard care are highlighted.

	T0: 0 weeks	T1: 1 week	T2: 3 weeks	T3: 6 weeks	T4: 3 months	T5: 6 months	T6: 9 months	T7: 12 months
PRWE-score	X			X	X	X	X	X
DASH	X			X	X	X	X	X
Frailty score		X						
PCS				X				
EQ-5D-score	X			X	X	X	X	X
Economic questionnaire				X	X	X	X	X
X-ray of wrist		X	X(bilateral)	X	X			
ROM				X	X	X		X
Grip strength				X	X	X		X

Table 1: Questionnaires at follow-up time points.

6.4 Withdrawal of individual subjects

Subjects can leave the study at any time for any reason if they wish to do so without any consequences. The investigator can decide to withdraw a subject from the study for urgent medical reasons.

Participants who leave the study, will be considered as a drop-out and will be contacted in order to obtain information about the reasons for this and will be checked for any adverse events.

6.5 Replacement of individual subjects after withdrawal

The number of patients who withdraw from the trial will not be replaced unless the number of anticipated loss to follow-up patients is exceeded. If informed consent is withdrawn, data collected so far will be used unless the patient explicitly asks to be removed from the study database. If patients cross over from one group to the other, patients will be asked to be

followed up to comply with the intention-to-treat principle so as to obtain a complete database of consecutive patients and to avoid attrition bias.

6.6 Follow-up of subjects withdrawn from treatment

Normal routinely follow-up at the outpatient clinic, standard control.

6.7 Premature termination of the study

This study will be terminated prematurely if and when patients experience an amount of discomfort or adverse events that is disproportionate to the benefit of the study and presents too great a risk to the participating study subjects.

7. SAFETY REPORTING

7.1 Section 10 WMO event

In accordance to section 10, subsection 1, of the WMO, the investigator will inform the subjects and the reviewing accredited METC if anything occurs, on the basis of which it appears that the disadvantages of participation may be significantly greater than was foreseen in the research proposal. The study will be suspended pending further review by the accredited METC, except insofar as suspension would jeopardize the subjects' health. The investigator will take care that all subjects are kept informed.

7.2 AEs, SAEs and SUSARs

7.2.1 Adverse events (AEs)

Both treatment groups represent options in standard treatment. We anticipate no treatment related risks related to participation in this study, but it is possible (though unlikely) that one treatment method will prove inferior to the other with respect to functional outcome.

Adverse events are defined as any undesirable experience occurring to a subject during the study, whether or not considered related to surgical intervention or non-operative closed reduction and casting. All surgery or cast treatment related adverse events spontaneously reported by patients or physicians other than pain, which is normal after a wrist fracture or surgery, will be recorded.

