Study design: Multi-center randomized controlled trial with a non-inferiority design and an economic evaluation alongside.

Study population: All consecutive patients aged 65 years and older with displaced intra-articular (AO Type C) distal radius fractures, with non-acceptable fracture characteristics within 3 weeks following trauma.

Intervention: Open reduction and internal fixation (intervention group) and plaster immobilization (control group).

Main study parameters: The primary outcome will be evaluated after 1 year with the Patient-Rated Wrist Evaluation score (PRWE).

Secondary outcomes comprise other patient reported outcome measures (PROMs) including the Disability of the Arm, Shoulder and Hand (DASH) and Quality of life (EQ-5D). Further outcome measurements comprise a costs evaluation questionnaire, range of motion (ROM), grip strength, radiographic parameters, Pain Catastrophizing Scale (PCS) and Complications.

Nature and extent of the burden: The treatment that study participants receive is a component of standard treatment of care. Prior research suggests there is no difference in long-term function between both treatment groups. Currently the choice of treatment is based on the preference of the surgeon, the complexity of the fracture and the national guideline for the treatment of radius fractures.

Post-operatively or after cast therapy patients will be seen 1 week, 3 weeks, 6 weeks, 3 months, 6 months and 12 months after trauma. The visits are standard care for patients following a fracture of the distal radius. After 6, 9 and 12 months depending on the treating physician's and/or patients' preference they can visit the hospital or can be visited at home. During these visits patients will be asked about complaints or complications, which is also part of regular care.

At baseline, and after 6 weeks, 3 months, 6 months, 9 months and 12 months patients will be asked to fill out 4 questionnaires mentioned earlier. These questionnaires can be filled out at home, online, or in the hospital prior to their visit and will take approximately 30 minutes for each of the 6 follow-up moments.

DART - Surgery vs. Casting for Displaced Articular Radius Fractures in Elderly

Prior to some visits, X-rays of the wrist will be made. The radiographs that are made during this study are all part of standard care.

In total study participants will spend 210 minutes to this study. This includes informed consent and the questionnaires.

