An x-ray of the wrist will be obtained prior to visits according to standard protocol, including one bilateral X-ray. Range of motion and grip strength will be tested at 6 weeks, 3 months, 6 months and 12 months.

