7.2.2 Serious adverse events (SAEs)

All serious adverse events will be described in patient file during consult at any of the follow-up visits or any other moment if indicated or requested by the patient. This includes deep and superficial wound infection, complex regional pain syndrome, compartment syndrome, any neurovascular or tendon damage.

All SAEs will be reported through the web portal ToetsingOnline to the accredited METC that approved the protocol, within 15 days after the sponsor has first knowledge of the serious adverse reactions.

SAEs that result in death or are life threatening should be reported expedited. The expedited reporting will occur not later than 7 days after the responsible investigator has first knowledge of the adverse reaction. This is for a preliminary report with another 8 days for completion of the report.

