8. STATISTICAL ANALYSIS

To answer our primary research question, whether the change in PRWE differs between treatment groups at 1 year after trauma, we will calculate the intervention effect using a mixed model, with intervention group and baseline PRWE as fixed factors and clusters (random factors) for repeated observations within patients and patients within hospitals (the latter only if a significant random intercept of hospital is observed).. Both crude and adjusted intervention effects will be calculated on an intention-to-treat and as-treated basis.

To further investigate the intervention effect over time, we will add time as fixed effect as well as an interaction between time and intervention group. , The secondary outcome variables will be analyzed in a similar way.

In additional analyses, we will investigate confounding and effect modification of several patient and fracture characteristics.

The primary outcome will be tested for non-inferiority with respect to the predefined threshold of 14 points on the PRWE, with a one-sided 97.5% confidence interval. For superiority analyses, a two-tailed value of $p < 0.05$ is considered to be significant.

COST EFFECTIVENESS ANALYSIS (CEA)

General considerations

Within this project, we will perform an economic evaluation that is in accordance with the most recent guidelines of “The National Health Care Institute”¹⁸.

Cost analysis

An economic evaluation will be performed from a societal as well as a healthcare perspective¹⁹. When the societal perspective is applied, all costs and consequences relevant to the intervention will be taken into account irrespective of who pays or benefits, whereas solely those accruing to the healthcare sector will be taken into account when the healthcare perspective is applied²⁰. Intervention costs will be estimated using a micro-costing approach¹⁸. Cost questionnaires will be administered on a 3-monthly basis to collect data on healthcare utilization, the use of informal care, and unpaid productivity losses.

Patient outcome analysis

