9.3 Benefits and risks assessment, group relatedness

The treatment that study participant receive is a component of standard treatment of care. Prior research suggests there is no difference in long-term function between both treatment groups. Currently the choice of treatment is based on the preference of the surgeon, the complexity of the fracture and the national guideline for the treatment of radius fractures.

Post-operatively or after cast therapy patients will be seen after 1 week, 3 weeks, 6 weeks, 3 months, 6 months and 12 months. These visits are standard care for patients following a fracture. In all these visits patients will be asked about complaints or complications, which is also part of regular care.

At baseline and after 6 weeks, 3 months, 6 months, 9 months and 12 months patients will be asked to fill out 4 questionnaires mentioned earlier as the main study parameters.

These questionnaires can be filled out at home online or in the hospital prior to their visit and will take approximately 30 minutes for each of these 6 data collection moments.

In total study participants will spend 210 minutes to this study. This includes informed consent and the questionnaires.

The risks of this study are comparable to risks involved with standard treatment. This comprises the standard risk for undergoing a surgical procedure, including risks related to anesthesia, neurovascular damage and post-operative wound infection. The risks of closed reduction and plaster immobilization include stiffness, redislocation, malunion, loss of function and complex regional pain syndrome.

Possible complications will be treated according to standard protocol.

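### Section 7.2.1 records only treatment-related, spontaneously reported adverse events, against its own definition and the enquiry at visits, so non-serious complications are open to arm-dependent recording

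*Protocol*

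**What the plan says.** Section 7.2.1 of the protocol counts an undesirable experience as an adverse event "whether or not considered related to surgical intervention or non-operative closed reduction and casting". The next sentence says what is recorded: "All surgery or cast treatment related adverse events spontaneously reported by patients or physicians other than pain".

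Two other places describe active enquiry. The Summary says: "During these visits patients will be asked about complaints or complications, which is also part of regular care". Section 9.3, after listing visits at 1, 3 and 6 weeks and 3, 6 and 12 months, says: "In all these visits patients will be asked about complaints or complications, which is also part of regular care".

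Section 7.2.2 handles serious events separately: "All serious adverse events will be described in patient file during consult at any of the follow-up visits", or at any other moment if indicated or if the patient asks. It adds: "This includes deep and superficial wound infection, complex regional pain syndrome, compartment syndrome, any neurovascular or tendon damage". Neither relatedness nor spontaneous reporting is a condition there.

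Complications is a secondary outcome. Section 6.1.2 lists it under the heading for change, beside DASH, EQ-5D, costs, range of motion and grip strength. It has no row in Table 1. For analysis, Section 8 says: "The secondary outcome variables will be analyzed in a similar way", where the model referred to is the mixed model for PRWE with its baseline value.

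**The concern.** A recording rule that depends on who volunteers an event, and on whether a physician ties it to treatment, is a weak basis for comparing arms in an open trial. One arm has an operation and the other a cast, so everyone who reports or attributes an event knows the treatment. An event after surgery and an event in a cast may not be attributed to treatment equally readily.

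The comparison matters beyond safety reporting. The Introduction states that complications are more likely after surgery, and the health care efficiency section gives a possible increase in complications as a reason to question it. If the cast proves non-inferior on PRWE, the complication rates will help decide which treatment is preferred. Section 6.7 also makes early termination depend on adverse events. Events that are not recorded at the visit cannot be recovered at analysis.

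**Working it through.** No figure in the protocol is at issue, so the check sets the passages side by side.

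**1. Which events are recorded.** Classify an event as serious or not, volunteered or elicited by asking, and judged related or unrelated.
- Serious: all four combinations fall under Section 7.2.2.
- Non-serious: all four meet the definition in Section 7.2.1, but only one (volunteered and related) meets its recording rule. The Summary and Section 9.3 say that patients are asked; neither says that the answers become trial data.

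**2. How far the serious-event list covers the named risks.** The Summary and Section 9.3 name the risks of each treatment.
- Surgery, three named: anaesthesia-related risks, neurovascular damage, wound infection. Two of the three are in the Section 7.2.2 list.
- Cast, five named: stiffness, redislocation, malunion, loss of function, complex regional pain syndrome. One of the five (the last) is in the list.

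The list is introduced as an inclusion and is not closed. A risk outside it reaches Section 7.2.2 only if it is otherwise judged serious; if not, the Section 7.2.1 rule applies.

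**3. Other routes to detection.** Table 1 schedules X-rays at 1, 3 and 6 weeks and 3 months, and range of motion at 6 weeks and 3, 6 and 12 months, in both arms. These would show redislocation, malunion and stiffness. Section 6.1.2, however, lists radiographic parameters as explanatory variables, and nothing says that X-ray or motion findings count as Complications.

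**4. Size.** Let r be a true risk equal in both arms, and let c_s and c_c be the shares of events recorded in the surgery and cast arms. The spurious difference is r × (c_s − c_c). The protocol gives none of the three, so these values are assumptions that show only how the result behaves:
- c_s = c_c: difference 0.
- r = 0.20, c_s = 0.9, c_c = 0.7: 0.18 − 0.14 = +0.04. With the shares exchanged: −0.04.
- r = 0.10 to 0.30, c_s = 0.9, c_c = 0.5: 0.10 × 0.4 = 0.04, to 0.30 × 0.4 = 0.12. With the shares exchanged: −0.04 to −0.12.

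The result runs from zero to 12 points in either direction, depending wholly on the assumed inputs. It is not an estimate for this trial.

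**5. Form of the outcome.** A complication has no baseline value, so a change in it has no meaning, and the PRWE model with its baseline term does not carry over literally. A similar minor wording point applies to two neighbouring items: "Range of motion and grip strength will be tested at 6 weeks, 3 months, 6 months and 12 months". They have no baseline measurement either.

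**The case against.** The strongest reply is that Section 7.2.1 is a safety-reporting rule and is nowhere named as the data source for the Complications outcome. Patients in both arms are asked about complications at visits, all serious events are captured without a filter, and X-rays and range of motion are scheduled alike in both arms. Stiffness, redislocation and malunion are named as risks of casting, so a physician has reason to attribute them to it. The rule also admits reports by physicians, who could pass on what they learn by asking.

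Much of this stands. A reader might infer that Complications as an outcome is captured solely through spontaneous, treatment-related reports; the documents do not say so, and Sections 7.2.2 and 9.3 speak against it. A reader might also infer that the secondary-outcome model cannot be fitted. That is too strong: a similar analysis need not be an identical one, it leaves room for a binary or count model or one without a baseline term, and a separate analysis plan may specify it.

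The reply does not remove the conflict. For non-serious events Section 7.2.1 is the only recording rule stated, no other source for the outcome is named, and the enquiry at visits is not tied to any record. If physicians pass on elicited events, the word spontaneous loses its meaning, but the relatedness filter remains.

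**Conclusion.** The point holds as a conflict between stated rules. Section 7.2.1 records less than it defines, disagrees with the enquiry described in the Summary and Section 9.3, and is narrower than Section 7.2.2. Non-serious complications, including most of the named cast risks unless judged serious, are therefore exposed to attribution and reporting made with knowledge of the arm.

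It is tempting to conclude that cast complications will be under-recorded, making surgery look worse by some number of points. The documents give neither complication risks nor recording rates by arm, so neither direction nor size follows; with equal recording there is no bias. The conclusion assumes only that Section 7.2.1 governs non-serious events, as its text says, and that treatment is known to those reporting.

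The reach is one secondary outcome and the review of non-serious safety events. The primary PRWE analysis is unaffected. The change is worth making because it is cheap and the missing data could not be recovered later.

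**What to change.** - **Section 7.2.1:** record all adverse events, related or not, elicited with the same checklist at the existing visits in both arms. Make relatedness a separate field, not a condition for recording. The exclusion of expected pain is not at issue here.
- **Sections 7.2.1 and 6.1.2:** state that this record, together with the serious adverse events, is the source of the Complications outcome. Bring the Summary and Section 9.3 into line.
- **Section 6.1.2:** take Complications out of the change heading. Reword range of motion and grip strength there as values at each visit.
- **Section 8:** compare the proportion of patients with at least one complication by 12 months between arms, with a 95% CI. That interval will be wide. At 57 per arm and an assumed risk of 20% in both, the half-width is 1.96 × √(2 × 0.20 × 0.80 / 57) = 0.147, about 15 points, before any loss to follow-up.

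The cost is a few sentences and a short checklist at visits that already take place. The downside is more minor events to record.

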7.2.2 Serious adverse events (SAEs)

All serious adverse events will be described in patient file during consult at any of the follow-up visits or any other moment if indicated or requested by the patient. This includes deep and superficial wound infection, complex regional pain syndrome, compartment syndrome, any neurovascular or tendon damage.

All SAEs will be reported through the web portal ToetsingOnline to the accredited METC that approved the protocol, within 15 days after the sponsor has first knowledge of the serious adverse reactions.

SAEs that result in death or are life threatening should be reported expedited. The expedited reporting will occur not later than 7 days after the responsible investigator has first knowledge of the adverse reaction. This is for a preliminary report with another 8 days for completion of the report.

7.3 Follow-up of adverse events

All AEs will be followed until they have abated, or until a stable situation has been reached. Depending on the event, follow up may require additional tests or medical procedures as indicated, and/or referral to the general physician or a medical specialist. SAEs need to be reported till end of study within the Netherlands, as defined in the protocol

8. STATISTICAL ANALYSIS

To answer our primary research question, whether the change in PRWE differs between treatment groups at 1 year after trauma, we will calculate the intervention effect using a mixed model, with intervention group and baseline PRWE as fixed factors and clusters (random factors) for repeated observations within patients and patients within hospitals (the latter only if a significant random intercept of hospital is observed).. Both crude and adjusted intervention effects will be calculated on an intention-to-treat and as-treated basis.

To further investigate the intervention effect over time, we will add time as fixed effect as well as an interaction between time and intervention group. , The secondary outcome variables will be analyzed in a similar way.

In additional analyses, we will investigate confounding and effect modification of several patient and fracture characteristics.

The primary outcome will be tested for non-inferiority with respect to the predefined threshold of 14 points on the PRWE, with a one-sided 97.5% confidence interval. For superiority analyses, a two-tailed value of $p < 0.05$ is considered to be significant.

COST EFFECTIVENESS ANALYSIS (CEA)

General considerations

Within this project, we will perform an economic evaluation that is in accordance with the most recent guidelines of “The National Health Care Institute”¹⁸.

Cost analysis

An economic evaluation will be performed from a societal as well as a healthcare perspective¹⁹. When the societal perspective is applied, all costs and consequences relevant to the intervention will be taken into account irrespective of who pays or benefits, whereas solely those accruing to the healthcare sector will be taken into account when the healthcare perspective is applied²⁰. Intervention costs will be estimated using a micro-costing approach¹⁸. Cost questionnaires will be administered on a 3-monthly basis to collect data on healthcare utilization, the use of informal care, and unpaid productivity losses.

Patient outcome analysis

Both a cost-effectiveness analysis in terms of the primary outcome (i.e. PRWE) and a cost-utility analysis (i.e. Quality Adjusted Life Years; QALYs) will be performed. For the cost-utility analysis, the patients’ health-related quality of life will be measured at baseline, 3, 6, 9, and 12-month follow-up using the EQ-5D-5L²¹. The patients’ EQ-5D-5L scores will be converted into utilities using a Dutch tariff. QALYs will subsequently be calculated using linear interpolation between time points, with higher QALY scores indicating more improvement in quality of life.

Statistical analyses

Economic evaluations will be performed in accordance with the intention-to-treat principle and missing data will be handled using multiple imputation²². Incremental Cost Effectiveness Ratios (ICERs) and Incremental Cost Utility Ratios (ICURs) will be calculated by dividing the differences in costs by those in effects/utilities. Analyses will be performed using linear multilevel analyses in order to account for the possible clustering of data²³. Bootstrapping techniques will be used to estimate uncertainty surrounding the cost-effectiveness estimates, while adjusting for potential confounders. Uncertainty will be shown in cost-effectiveness planes and cost-effectiveness acceptability curves. Sensitivity analyses will be performed to test the robustness of the results (e.g. per-protocol analysis)^{20,24}.

BUDGET IMPACT ANALYSIS (BIA)

General considerations

Within this project, we will perform a budget impact analysis that is in accordance with the most recent guidelines of “The National Health Care Institute”¹⁸.

Cost analysis

In the budget impact analysis, the size and characteristics of the people aged 65 or older that suffer from a distal radius fracture will be estimated using Dutch epidemiological data. The effectiveness of the treatments will be extrapolated using a simple Markov model based on the estimates obtained in the proposed study. Within these analyses, the societal, healthcare, and insurer perspective will be considered. Monetary valuations will differ between these perspectives and different implementation scenarios will be evaluated.

